9.6.2 Adverse Events and Disease-related Events

Subject incidence of all treatment-emergent adverse events will be tabulated by system organ class and preferred term. Tables of fatal adverse events, serious adverse events, adverse events leading to withdrawal from investigational product or other protocol-required therapies, and significant treatment emergent adverse events will also be provided. Subject incidence of disease-related events and fatal disease-related events, if applicable, will be tabulated by system organ class and preferred term. Disease-related events will be combined with other adverse events for the tabulations.

The Medical Dictionary for Regulatory Activities (MedDRA) version **21.1** or later will be used to code all events categorized as adverse events, disease-related events, endpoints, to a system organ class and a preferred term.

The subject incidence of adverse events will be summarized for all treatment-emergent adverse events, serious adverse events, adverse events leading to withdrawal of investigational product, fatal adverse events, and adverse events of interest.

Subject incidence of all treatment-emergent adverse events, serious adverse events, treatment-related serious and non-serious adverse events, disease-related events, adverse events leading to withdrawal of investigational product, and fatal adverse events will be tabulated by system organ class and preferred term in alphabetical order.

Summaries of treatment-emergent and serious adverse events occurring in at least 5% of the subjects by preferred term in any treatment arm will be provided in descending order of frequency.

Summaries of treatment-emergent and serious adverse events will be tabulated by system organ class, preferred term, and grade.

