#### **9.2.3.1 Adverse Events**

##### **9.2.3.1.1 Time Period and Frequency for Collecting and Reporting Safety Event Information**

###### **9.2.3.1.1.1 Disease-related Events**

Migraine and headache are study disease-related events and thus should not be routinely reported as (serious) adverse events unless assessed to be more severe than expected for the subject. Disease-related events are defined in [Appendix 4](#).

The investigator is responsible for ensuring that all disease-related events observed by the investigator or reported by the subject that occur after the first dose of investigational product(s)/study treatment/protocol-required therapies through 18 weeks after the last dose of investigational product (EOS) are reported using the Event CRF.

Disease-related events assessed by the investigator to be more severe than expected and/or related to the investigational product(s)/study treatment/protocol-required therapies, and determined to be serious, must be reported on the Event CRF as serious adverse events.

Disease-related events pre-defined for this study include: migraine and headache and should not be routinely reported as (serious) adverse events unless assessed to be more severe than expected for the subject.

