#### **10.4.3 Methods of Analyses**

##### **10.4.3.1 General Considerations**

The primary objective of this study is to evaluate the effect of AMG 301 compared to placebo on the change from the baseline period in monthly migraine days, in subjects with CM or EM.

Summary statistics by each treatment group will be tabulated at each visit. For continuous endpoints, the descriptive statistics include: number of observations, means, medians, standard deviations, standard errors, first and third quartiles, minimums and maximums, and 2-sided 95% confidence intervals of the means (confidence intervals will be provided for efficacy endpoints only). For categorical endpoints, the summaries will contain the number and percentage of subjects in each category.

CCI

Details of all statistical methods will be provided in the Statistical Analysis Plan.

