#### 10.4.3.3.2 Adverse Events and Disease-related Events

Subject incidence of all treatment-emergent adverse events will be tabulated by system organ class and preferred term. Tables of fatal adverse events, serious adverse events, adverse events leading to withdrawal from investigational product or other protocol-required therapies, and significant treatment emergent adverse events will also be provided. Subject incidence of disease-related events, fatal disease-related events, and device-related events, if applicable, will be tabulated by system organ class and preferred term.

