## Appendix 4. Safety Events: Definitions and Procedures for Recording, Evaluating, Follow-up and Reporting

Disease-related Event Definition

• Disease-related events are events (serious or non-serious) anticipated to occur in the study population due to the underlying disease. See Section 9.2.3.1.1.1 for the list of disease-related events.

• Disease-related events that would qualify as an adverse event or serious adverse event:

○ An event based on the underlying disease that is worse than expected as assessed by the investigator for the subject's condition or if the investigator believes there is a causal relationship between the investigational product(s)/study treatment/protocol-required therapies and disease worsening, this must be reported as an adverse event or serious adverse event.

• Disease-related events that do not qualify as adverse events or serious adverse events:

○ An event which is part of the normal course of disease under study (eg, disease progression in oncology or hospitalization due to disease progression) is to be reported as a disease-related event.

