- Change from baseline in monthly mean overall impact on everyday activities as measured by the MPFID stand-alone item
- Change from baseline in monthly days with impact on everyday activities as measured by the MPFID domain
- Change from baseline in monthly days with physical impairment as measured by the MPFID domain
- Change from baseline in the Cranial Autonomic Parasympathetic Symptom (CAPS) scale total score
- Change from baseline in monthly migraine-related disability and productivity as measured by MMIDAS
- Change from baseline in daily activity impact of headache as measured by HIT-6
- Change from baseline in the first 4 weeks in monthly migraine days

Change from Baseline in Mean Monthly Efficacy Measurement over Multiple Months

- The Change from Baseline in Mean Monthly Efficacy Measurement is the Arithmetic mean of monthly values for the months considered - baseline monthly value

Percent Change from Baseline

The change from baseline divided by baseline and multiplied by 100:

$$(\text{Post-baseline} - \text{Baseline}) * 100 / \text{Baseline}$$

If the baseline value is 0 and the post-baseline value is also 0, then the percent change from baseline is set to 0. If the baseline value is 0 and the post-baseline value is non-zero, then the percent change from baseline is set to be missing

Percent change from baseline in (mean) monthly migraine days which is used to determine 50%, 75%, and 100% responder will be calculated as above.

Subject Incidence

The subject incidence for a given event in a given period is defined as the number of subjects with at least one reported occurrence of the event divided by the number of

subjects who entered that period. For subjects with multiple occurrences of the same event, the event will only be counted once per subject.

Medication Overuse at baseline

Medication overuse at baseline will be considered if any of the following criteria are present:

- **≥ 15 days of simple analgesic,**
- **≥ 10 days of triptans,**
- **≥ 10 days of ergotamines,**
- **≥ 10 days of combination therapy intake of any combination of ergotamines, triptans, opiates, combination-analgesic medication (includes the case of more than 1 medication category within one visit).**

Medication Overuse during the DBTP

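### SAP 9.6.2 does not say which adverse event tables take in disease-related events, so a TEAE table without them should be added; separately, protocol Appendix 4 holds two opposite rules on lack of efficacy

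*SAP*

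**What the plan says.** **Pooling of disease-related events.** SAP 9.6.2 first plans a display of these events: "Subject incidence of disease-related events and fatal disease-related events, if applicable, will be tabulated by system organ class and preferred term". The next sentence reads "Disease-related events will be combined with other adverse events for the tabulations". A later paragraph of the same section lists the tables by system organ class and preferred term, and disease-related events appear there as an item of their own, among "treatment-related serious and non-serious adverse events, disease-related events, adverse events leading to withdrawal of investigational product".

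The protocol treats these events as a separate class. Section 9.2.3.1.1.1 says "Migraine and headache are study disease-related events and thus should not be routinely reported as (serious) adverse events", with an exception for events more severe than expected for the subject. Appendix 4 has a category headed "Disease-related events that do not qualify as adverse events or serious adverse events", which holds events in the normal course of the disease. Protocol 10.4.3.3.2 plans "Subject incidence of disease-related events, fatal disease-related events, and device-related events, if applicable, will be tabulated by system organ class and preferred term" and has no pooling sentence.

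Both classes are entered on the Event CRF. SAP 5.1.2 identifies disease-related events by a flag there and defines a TEAE from the same CRF page. SAP 2.1 makes TEAE incidence a secondary endpoint.

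**Lack of efficacy.** Protocol Appendix 4, in the list of events meeting the adverse event definition, says that lack of efficacy in itself is not reported as an adverse event or serious adverse event. A stand-alone OR follows, and the next bullet says that it does count as one.

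**The concern.** In this trial the disease-related events are migraine and headache, and the efficacy outcome is migraine days. If they enter the TEAE tables, the displayed incidence by arm can move for reasons unrelated to harm. An effective drug could lower the pooled incidence in the active arm and so offset a real excess of other adverse events; an ineffective one would leave a shared background that makes the arms look more alike. Rows for preferred terms other than migraine and headache are not affected.

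The second point concerns data collection. Two sites that each follow Appendix 4 could record the same lack of efficacy in opposite ways, which would change adverse event counts.

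**Working it through.** There is no planned figure to reproduce: the documents give no adverse event or disease-related event rates. The check compares the passages, then adds a bound and an illustration on assumed rates.

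**Which tables are pooled?**
- SAP 9.6.2 refers only to the tabulations in general.
- The sentence directly follows the one on the disease-related event display, so it could concern that display alone. Its wording could equally cover every adverse event table.
- The later separate listing of disease-related events suggests that not everything is pooled.
- SAP Table 9-3 describes the TEAE, serious, withdrawal and fatal tables without mentioning pooling.
- The TEAE definition in SAP 5.1.2 does not say whether flagged records count.

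The scope is therefore undefined, and the content of the TEAE tables depends on how the programmer reads one sentence.

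**What a reader of pooled tables could recover.** Let U be the pooled any-event incidence in an arm, d the disease-related event incidence and A the incidence of adverse events alone. SAP 5.6 says "For subjects with multiple occurrences of the same event, the event will only be counted once per subject", and a subject may have both kinds of event, so subtracting d from U does not give A. It gives only

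U − d ≤ A ≤ U.

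From those two rows, the between-arm difference in A is known to within a range of width d(placebo) + d(active). No independence is assumed. The values of d and U below are assumptions:

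| d per arm | U placebo / active | A placebo | A active | Range for active − placebo | Width |
|---|---|---|---|---|---|
| 5% | 47.75 / 62.00 | 42.75 to 47.75 | 57.00 to 62.00 | 9.25 to 19.25 | 10 points |
| 30% | 61.5 / 72.0 | 31.5 to 61.5 | 42.0 to 72.0 | −19.5 to 40.5 | 60 points |

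Other rows of the tables may narrow these ranges.

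**Illustration, assuming independence.** U = 1 − (1 − A)(1 − d). With equal d in both arms, the displayed difference is (1 − d) times the difference in A. Take A of 45% on placebo and 60% on active, a 15-point difference:
- d = 5%: 0.95 × 15 = 14.25 points.
- d = 30%: 0.70 × 15 = 10.5 points.

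With A of 50% in both arms and unequal d:
- d of 30% placebo, 20% active: U is 65% and 60%, a difference of −5 points.
- d of 20% placebo, 30% active: U is 60% and 65%, a difference of +5 points.

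The direction can go either way, and the effect is small if few disease-related events are recorded. The documents do not settle how many there will be. Protocol 9.2.3.1.1.1 asks for all of them on the Event CRF up to 18 weeks after the last dose, and eligibility requires at least 4 baseline migraine days, so a literal reading allows a high rate. Actual recording practice is unknown.

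**Lack of efficacy.** The two bullets agree that signs, symptoms and sequelae meeting the definition are reported. They conflict only on lack of efficacy in itself. Section 9.2.3.1.1.1 and the disease-related event definition govern migraine and headache events, which narrows the practical gap, but neither chooses between the bullets.

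**The case against.** The strongest reply is that the harm assumes one reading of an unclear sentence. Table 9-3 does not mention pooling and disease-related events have their own display, so the TEAE tables may never be pooled. That stands: the problem is conditional.

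A reader might also infer that the incidence of adverse events alone is lost. It is not. The flag exists, so at most a row is not displayed, and the widths above apply to someone working from printed tables, not to the sponsor with the data. Every rate behind those widths is assumed. SAP 9.6.2 also keeps a treatment-related tabulation, and Appendix 4 requires disease worsening thought to be caused by the product to be reported as an adverse event, so drug-related worsening is not hidden.

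A third inference is that the SAP reverses the protocol and had to declare this in SAP Section 10. The protocol nowhere says that adverse event tables exclude disease-related events, and its section 10.4.3.1 says "Details of all statistical methods will be provided in the Statistical Analysis Plan". Section 10 of the SAP does not list the pooling, but that omission is a weak charge.

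Finally, pooling can be defended as the more inclusive safety display. Disease-related events may be serious, and taking them out of the serious adverse event tables would rest on the investigator's judgement of what was expected. This also stands: pooled tables should be supplemented, not replaced.

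On the second point, the text may be unedited template wording and its link to any analysis is slight. That limits its weight but does not remove the contradiction.

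**Conclusion.** Both points hold, within limits.

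First, SAP 9.6.2 leaves open whether disease-related events count in the TEAE tables. If they do, parts of a secondary endpoint mix harm with the efficacy outcome, and the incidence of adverse events alone is not shown. The size cannot be determined from the documents; the 5% and 30% cases show only how it scales with an assumed rate. No treatment comparison of safety is tested, so alpha, power and the primary endpoint are untouched. That the incidence can be derived rests on the flag separating events recorded only as disease-related from those also reported as adverse events, which the SAP does not explain.

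Second, Appendix 4 is contradictory as written on lack of efficacy in itself, and on nothing wider. Its effect on counts is not quantified.

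The sponsor should act on both. Neither threatens the efficacy conclusion.

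**What to change.** **SAP 9.6.2.**
- Name the tables that combine adverse events and disease-related events. Keep them, including any pooled serious adverse event tables, and label them as combined.
- Add a TEAE incidence table by arm that excludes events recorded only as disease-related. First confirm how the Event CRF flag marks a disease event that was also reported as an adverse event.
- Keep the planned separate disease-related event table.
- Listing the pooling rule in SAP Section 10 is optional.

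Cost: SAP wording, some programming and a few extra tables. No new data are needed if the flag separates the events as required.

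**Protocol Appendix 4.** The sponsor must reconcile the two bullets on lack of efficacy into one rule and give it to all sites through a protocol amendment. This review does not say which rule is right. Cost: an amendment, with ethics committee submission and approval where necessary under Appendix 3, so more than an editorial correction.

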9.6.3 Laboratory Test Results

Shift tables of the laboratory toxicity based in CTCAE grade will be tabulated by treatment group. Subject listing of grades ≥ 2 laboratory toxicities will be provided. In the cases when CTCAE grading scales include numeric range in combination with clinical assessment (eg Potassium [Hypokalemia]), laboratory test results may be summarized based on standard normal ranges or by CTCAE grade utilizing investigator's input.

Summary of change from baseline in selected lab analyst will also be provided.

Subject incidence of liver function test abnormalities (including AST, ALT, Total Bilirubin (TBL) and Alkaline Phosphatase (ALP)) will also be summarized by treatment group.

Additional liver test summary table will provide the number and percentage of subjects by treatment group for the following categories:

- AST and ALT ($> 3x$ ULN; $> 5x$ ULN; $> 10x$ ULN; $> 20x$ ULN, respectively)
- AST or ALT ($> 3x$ ULN; $> 5x$ ULN; $> 10x$ ULN; $> 20x$ ULN, respectively)
- Total Bilirubin ($> 1x$ ULN; $> 1.5x$ ULN; $> 2x$ ULN, respectively)
- ALP (> 1.5 ULN)
- ALT or AST $> 3x$ ULN and Total Bili $\geq 2x$ ULN and ALP $< 2x$ ULN

Subject incidence of elevated HbA1c $\geq 6.0\%$ over the DBTP and safety follow-up period will also be summarized by treatment group.

9.6.4 Vital Signs

The analyses of vital signs (systolic/diastolic blood pressure, heart rate, temperature and respiratory rate) will include summary statistics of change from baseline over time by treatment group.

Systolic and diastolic blood pressure will also be analyzed by change from baseline in categories: ≥ 20 mm Hg in SBP for SBP > 140 mm Hg (Yes vs. No) and ≥ 10 mm Hg in DBP for DBP > 90 mm Hg (Yes vs. No) at each time point.

The number and percentage of subjects with at least one post-treatment vital sign measurement meeting any of the following criteria will be reported:

- Systolic Blood Pressure: < 90 mm Hg, > 140 mm Hg, > 160 mm Hg
- Diastolic Blood Pressure: < 50 mm Hg, > 90 mm Hg, > 100 mm Hg
- Pulse Rate: < 60 bpm, > 100 bpm
- Temperature: $> 38.0^{\circ}\text{C}$, $< 36.0^{\circ}\text{C}$
- Respiratory rate: < 12 breaths/min, > 20 breaths/min

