### Other Medical Conditions

205 Currently diagnosed with chronic pain syndromes (eg, fibromyalgia, chronic back pain, chronic pelvic pain)

206 History of major psychiatric disorder, (such as schizophrenia and bipolar disorder), or current evidence of depression based on a Beck Depression Inventory II (BDI-II) total score > 19 at screening. Subjects with anxiety disorder and/or major depressive disorder are permitted in the study if the investigator considers the subject to be stable (with BDI-II  $\leq$  19) and are taking no more than 1 medication for each disorder. Subjects must have been on a stable dose within the 2 months before the start of the baseline period.

207 History of seizure disorder or other significant neurological conditions other than migraine. Note: A single childhood febrile seizure is not exclusionary.

208 Malignancy within the 5 years before screening, except non-melanoma skin cancers, cervical or breast ductal carcinoma in situ.

209 Known human immunodeficiency virus infection by history

210 Hepatic disease by history or total bilirubin  $\geq$  1.5 x upper limit of normal (ULN) or alanine aminotransferase (ALT) or aspartate aminotransferase (AST)  $\geq$  2.0 x ULN, as assessed by the central laboratory at screening.

211 Glycosylated hemoglobin (HbA1c)  $\geq$  6.0% at screening

212 **Serum plasma glucose level  $\geq$  100 mg/dL at screening; ideally performed while fasting**

213 History of diabetes mellitus or history of impaired fasting glucose

- 214 Body mass index (BMI) ≤ 18.0 or ≥ 40 at screening
- 215 Poorly controlled hypertension (systolic blood pressure 150 mmHg and/or diastolic blood pressure 90 mmHg or greater)
- 216 Myocardial infarction, stroke, transient ischemic attack, unstable angina, or coronary artery bypass surgery or other revascularization procedure within 12 months before screening
- 217 History or evidence of any other unstable or clinically significant medical condition that, in the opinion of the investigator, would pose a risk to subject safety or interfere with the study evaluation, procedures, or completion
- 218 Subject has any clinically significant vital sign, laboratory, or electrocardiogram (ECG) abnormality during screening that, in the opinion of the investigator, could pose a risk to subject safety or interfere with the study evaluation

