#### **10.4.3.3.4     Vital Signs**

The analyses of vital signs will include summary statistics over time by treatment group. Shifts in vital sign values between the baseline and the worst on-study value will be tabulated by treatment group.

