9.7.2 Analyses of Clinical Outcome Assessments

See Section 9.5.4.

10. Changes From Protocol-specified Analyses

The endpoint of change from the baseline period in monthly days with impact on everyday activities as measured by the MPFID domain at assessment time points was not included in the protocol but was added to the SAP to assess the effect of AMG 301 compared to placebo on change from the baseline period in monthly days with impact on everyday activities as measured by the MPFID domain.

The protocol stated that for secondary endpoints comparison between treatment groups for categorical data will be performed using generalized linear mixed effects model on observed data adjusting for baseline values and stratification factors with appropriate contrasts for pairwise comparisons as well as CMH test. The analysis method will be changed so that comparison between treatment groups for secondary endpoints will be performed using only CMH tests on observed data with stratification factors for categorical data.

The protocol stated that the FAS consists of all subjects who were enrolled in the study. This definition will be changed so that the FAS consists of all subjects who were randomized in the study.

Three subgroups were added: prior use of anti-CGRP medication, CAPS score at baseline, and response status to AMG 334.

11. Literature Citations / References

AMG 301 Investigator Brochure. Thousand Oaks, CA. Amgen Inc.

Amgen. A Phase 2, Randomized, Double-blind, Placebo-controlled Study to Evaluate the Efficacy and Safety of AMG 334 in Chronic Migraine Prevention. AMG 334 Study 20120295. 23 July 2015.

Amgen. A Phase 3, Randomized, Double-blind, Placebo-controlled Study to Evaluate the Efficacy and Safety of AMG 334 in Migraine Prevention. AMG 334 Study 20120296. 24 March 2015.

Edvinsson L. Role of VIP/PACAP in primary headaches. *Cephalgia* 2013;33:1070-1072.

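### The SAP omits the protocol's baseline-to-worst vital-sign shift table without declaring it, and its threshold counts mix values already present at baseline with new ones

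*SAP*

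**What the plan says.** Protocol 10.4.3.3.4 plans two vital-sign analyses: summary statistics over time, and a shift table. On the second it says: "Shifts in vital sign values between the baseline and the worst on-study value will be tabulated by treatment group".

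SAP 9.6.4 plans three:

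- For blood pressure, heart rate, temperature and respiratory rate, analyses that "will include summary statistics of change from baseline over time by treatment group".
- For high blood pressure only, a category at each time point that combines a rise with a high value: "≥ 20 mm Hg in SBP for SBP > 140 mm Hg (Yes vs. No"), and the diastolic counterpart (a rise of at least 10 mm Hg with a value above 90).
- A threshold count: "The number and percentage of subjects with at least one post-treatment vital sign measurement meeting any of the following criteria will be reported". The limits are absolute, for example "Pulse Rate: < 60 bpm, > 100 bpm". The others are SBP below 90, above 140 and above 160; DBP below 50, above 90 and above 100; temperature below 36.0 or above 38.0 °C; and respiratory rate below 12 or above 20.

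The SAP keeps shift tables elsewhere. For laboratory data, SAP 9.6.3 says: "Shift tables of the laboratory toxicity based in CTCAE grade will be tabulated by treatment group". SAP Table 9-2 has severity-grade shifts for HIT-6 and the modified MIDAS.

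SAP Section 10 lists the changes from the protocol: an added MPFID endpoint, the move to CMH tests, the definition of the FAS, and, last, "Three subgroups were added: prior use of anti-CGRP medication, CAPS score at baseline, and response status to AMG 334". It has no entry on vital signs.

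**The concern.** A baseline-to-worst shift table answers a subject-level question: of those who were within limits before dosing, how many went outside them? The threshold count answers a different one: how many subjects had a value outside the limits at any time after treatment, whatever they had before? Without the baseline cross-tabulation, a reader of the count cannot separate long-standing from new values.

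Vital signs are a named secondary safety endpoint, which SAP 2.1 defines as change from baseline. Protocol 3.3 describes the target's ligand as vasoactive and relies on vital signs to monitor respiratory and cardiovascular effects and homeostatic control. A table that shows who moved out of range is useful for that purpose, and the protocol already promised one.

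**Working it through.** **Step 1: is the shift table missing?** Set side by side, the protocol section has summary statistics plus shifts, and the SAP section has change summaries, blood-pressure rise categories and threshold counts. The SAP's only shift tables are for laboratory grades, HIT-6 and the modified MIDAS. Nothing is blacked out in either vital-signs section. The table is absent, and Section 10 does not say so.

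**Step 2: can pre-existing values enter the count?** The rule requires only one post-treatment value past the limit.

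- *High systolic pressure.* The entry limit is "Poorly controlled hypertension (systolic blood pressure 150 mmHg and/or diastolic blood pressure 90 mmHg or greater"). Taking the words on greater values to cover both pressures, SBP of 141 to 149 is allowed at screening and already meets the above-140 criterion. SBP above 160, DBP above 90 and DBP above 100 are excluded at screening.
- *Pulse, temperature, respiratory rate, low blood pressure.* No eligibility criterion sets a numeric limit. Exclusion 218 leaves clinically significant abnormalities to the investigator's judgement.

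**Step 3: which signs have a subject-level category that uses baseline?**

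| Sign | Mean change | Category using baseline |
|---|---|---|
| High SBP, high DBP | yes | yes, by time point, not worst value |
| Low SBP, low DBP | yes | none |
| Pulse | yes | none |
| Temperature | yes | none |
| Respiratory rate | yes | none |

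**Step 4: how much dilution?** The documents give no figure to reproduce and no prevalence or onset rate, so what follows is illustration on assumed inputs.

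In the placebo arm let P be the proportion flagged who were already past the limit at baseline, and N the proportion newly flagged. Suppose a dose doubles N and leaves P unchanged. The ratio of flagged proportions is (P + 2N)/(P + N) = 2 − s, where s = P/(P + N) is the pre-existing share of flagged placebo subjects.

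*Assumption set A.* New-onset rates are 5% on placebo and 10% on a dose among those within limits at baseline, and every pre-existing case recurs. Flagged proportion = pre + (1 − pre) × rate.

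| Pre-existing | Placebo | Dose | s | Ratio | Difference (points) |
|---|---|---|---|---|---|
| 10% | 14.5% | 19.0% | 0.10/0.145 = 0.69 | 1.31 | 4.5 |
| 15% | 19.25% | 23.5% | 0.15/0.1925 = 0.78 | 1.22 | 4.25 |
| 25% | 28.75% | 32.5% | 0.25/0.2875 = 0.87 | 1.13 | 3.75 |

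Among subjects within limits at baseline, the ratio is 2.0 and the difference 5.0 points.

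*Assumption set B.* This is a simulation with no drug effect and the 11 scheduled post-dose measurements (day 1 post-dose; weeks 2, 4, 6, 8, 10, 12, 16, 20, 24 and 28), taking all of them as post-treatment. Within-subject correlation is 0.5 to 0.7.

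| Criterion | Assumed mean, SD | Flagged at least once | s | 2 − s |
|---|---|---|---|---|
| Pulse below 60 | 68–76, 10 | 21–65% | 0.16–0.38 | 1.62–1.84 |
| SBP above 140 (screening below 150) | 115–125, 13 | 12–47% | 0.11–0.27 | 1.73–1.89 |

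A doubling is impossible in one pulse setting (mean 68, correlation 0.5): 45.5% of all subjects are newly flagged and only 78.9% start at or above 60, so 2 × 45.5% = 91.0% is too many. Removing that setting does not change the ranges for s or 2 − s.

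The two sets differ because repeated measurement flags many subjects through ordinary fluctuation, which lowers the pre-existing share. Together they span 1.13 to 1.89, too wide to name a figure for this trial.

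**The case against.** The strongest reply is that the SAP does analyse vital signs against baseline. The change summaries cover every sign by arm, and SAP 9.1 includes quartiles, minimum and maximum, so the largest fall or rise at each visit is visible. That matches the stated endpoint, and the threshold count is an addition. High blood pressure has its own rise categories, and most high-pressure cut-offs cannot be met at screening. Clinically significant vital-sign abnormalities, including those that worsen from baseline, are adverse events under protocol Appendix 4 and are tabulated by arm. A Data Review Team reviews safety by treatment group.

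All of that stands, and it rules out the claim that pulse, temperature, respiratory rate and low blood pressure have no baseline-related analysis. It does not supply the missing table: extremes of change at a visit do not count how many subjects crossed a limit, and adverse-event reporting depends on the investigator's judgement.

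A reader might also infer that the count hides a real difference between arms. The documents do not support that. Randomisation spreads pre-existing values across arms by chance, SAP 9.6.1 rules out testing of safety data, and the ratios above rest on assumed inputs. In set A, 69% to 87% of flagged placebo subjects are pre-existing, well above the 11% to 38% in set B, and the absolute difference shrinks by only 0.5 to 1.25 points. Nor does the SAP label the counted values as new or treatment-emergent; the risk is that a reader takes them so.

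Finally, the protocol promises only a shift table and defines no categories for it. Splitting the threshold counts by baseline status goes beyond what it requires and is a recommendation.

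**Conclusion.** The point holds as a modest one. A descriptive safety table promised in the protocol is absent from the SAP, and the SAP's list of changes does not say so. The threshold table that is planned mixes pre-existing with new values in every arm, and for pulse, temperature, respiratory rate and low blood pressure no other subject-level category uses baseline.

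The consequence is possible dilution of relative contrasts and misattribution of long-standing values. It is not bias between arms, and no hypothesis test is affected. The omission and the counting rule are read directly from the text and need no assumption. The size does: it depends on how many subjects start past each limit and how often others cross it, neither of which the documents give.

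**What to change.** In SAP 9.6.4, restore a table of baseline category by worst post-baseline category for each vital sign, by treatment group, using the SAP's existing cut-offs. For signs with limits on both sides, define worst separately for low and high. Show each threshold count by whether the subject met that criterion at baseline, or add a count among those who did not, with their number as the denominator. If the sponsor prefers to drop the shift table, SAP Section 10 should record and justify that.

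The cost is a few extra tables and slightly smaller denominators. Baseline is already defined in SAP 5.3 and the measurements are already scheduled, so no new data are needed. One limit remains: with a single baseline value and up to 11 later ones, ordinary fluctuation still moves subjects past a limit. In set B, about 16% to 46% of all subjects were newly flagged for low pulse with no drug effect, so the counts still have to be read against placebo.
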